5.2. Instructions for Use and Administration

5.2.1. Route of administration

The NTX Neuromodulation System is designed to stimulate the common peroneal nerve; stimulation electrodes within the device are positioned superficially and bilaterally on the lower legs over the head of the fibula bone, a position where the peroneal nerve is closest to the skin. This nerve target innervates regions of the lower extremities commonly associated with RLS symptoms.

5.2.2. Dosage and dosage regimen

The dosage depends on the intensity and duration of stimulation:

1. Setpoint stimulation intensity. The setpoint stimulation intensity will be the lesser of (a) the maximal intensity that the subject reports is non-distracting and comfortable, as determined in the calibration session described in the instructions for device use and (b) the maximal intensity for each set of stimulation parameters, as determined based on device output capabilities.
2. Participants will be allowed to adjust stimulation intensity from the setpoint, but only within a limited pre-programmed range. For example, participant may increase intensity if symptoms are severe or reduce intensity if symptoms are mild.
3. Participants may be instructed to administer stimulation each night or only administer stimulation when RLS symptoms are present.
4. Stimulation may be activated for up to 120 minutes per day, depending on the timing, duration, and severity of RLS symptoms for the specific subject.

5.3. Contraindications

The following are contraindications to device usage:

- Diagnosis of epilepsy or other seizure disorder,
- Active medical device implant anywhere in the body, including but not limited to pacemakers, spinal cord stimulators, deep brain stimulators

CONFIDENTIAL

All information contained in this document is confidential and is the sole property of Noctrix Health, Inc.
Any reproduction in part or whole without the written permission of Noctrix Health, Inc. is prohibited.

 NOCTRIX HEALTH	Clinical Trial Investigational Plan, Protocol CT-03 (Opioid Reduction Study)	Document #: CT-2 (Previously CT-03) Rev: 4.0 (Superseded Rev C) CC#: 720 (Previously DCO #138) Effective: 09/24/2021
---	---	---

- Metal implant at the site of study device electrode application
- Known allergy to device materials (or severe previous reaction to medical adhesives or bandages)
- Cellulitis, open sores, or acute injury at or near the location of device electrode application

6. Risks

6.1. Investigational device risks

NPNS devices such as NTX Neuromodulation System result in a known potential for the following anticipated observations, which are typically mild to moderate, transient in nature, and resolve over time.

- Mild skin irritation from use of adhesive electrodes and/or secondary attachment mechanism.
 - *This risk is reduced by calibrating the stimulation intensity.*
- Discomfort, paresthesia, or otherwise irritating or uncomfortable sensations during active electrical stimulation.
 - *This risk is reduced by calibrating the stimulation intensity.*
- Temporary interference with sleep while wearing the device:
 - For some individuals, device may be uncomfortable, thus interfering with sleep while wearing the device.
 - For some individuals, this device may interfere with preferred sleep positions, thus interfering with sleep during usage.
- Temporary increase in RLS symptoms while wearing the device:
 - For some individuals, this device may interfere with voluntary leg movements used to relieve RLS symptoms, thus leading to a temporary increase in RLS symptoms.
 - In some cases, this device may otherwise lead to a temporary increase in RLS symptoms during active stimulation for other reasons.
 - *This risk may be reduced by calibrating the stimulation intensity and/or adjusting the schedule of stimulation.*

CONFIDENTIAL

All information contained in this document is confidential and is the sole property of Noctrix Health, Inc.
 Any reproduction in part or whole without the written permission of Noctrix Health, Inc. is prohibited.

 NOCTRIX HEALTH	Clinical Trial Investigational Plan, Protocol CT-03 (Opioid Reduction Study)	Document #: CT-2 (Previously CT-03) Rev: 4.0 (Superseded Rev C) CC#: 720 (Previously DCO #138) Effective: 09/24/2021
---	---	---

6.2. Risks associated with study procedures

6.2.1. Opioid withdrawal procedure

Opioid withdrawal symptoms can occur during dosage reduction, specifically for rapid dosage reduction of short-acting, high-dose opioids. In contrast, the protocol here involves gradual dosage reduction (approximately 25% per week) of primarily long-acting (e.g. methadone, oxycodone), and exclusively low-dose (below 60 MME) opioids. Therefore, we expect a low risk of opioid withdrawal symptoms. However, it is possible that one or more symptoms that are associated with opioid withdrawal [11] may occur, such as the following: agitation, restlessness, and anxiety, depression, insomnia, yawning, increased tearing or watery eyes, runny nose, sweating, shivering, trembling, or goosebumps, muscle aches or joint pain, nausea or vomiting, abdominal cramps, diarrhea. Subjects will undergo a weekly investigator assessment and subjects with clinically significant withdrawal symptoms will be excluded from further participation. Moreover, subjects with intolerable withdrawal symptoms will have the option to discontinue participation at any time and revert to their original opioid dosage.

7. Adverse Events

Anticipated observations (e.g. common treatment effects) and adverse events occurring during the study will be recorded. Descriptions of anticipated observations and AEs will include the date of onset, the date it ended, the severity, the relationship to study device, and the outcome. All reported AEs will be summarized by the number of subjects reporting AEs, system organ class (where applicable), severity, seriousness, and relationship to study device.

The study Investigator and Coordinator will evaluate, characterize and record in the Case Report Form (CRF) all adverse events (AEs) occurring in all subjects from the time of enrollment to study exit (or premature withdrawal). Adverse events unresolved at study exit will be followed by the Investigator until resolution occurs or at least 60 days after the subject's participation in the study is complete. AEs may be reported spontaneously by the subject or detected by the Investigator or Coordinator. AEs should be evaluated for diagnoses not just symptoms (i.e., "angina", not "chest pain").

CONFIDENTIAL

All information contained in this document is confidential and is the sole property of Noctrix Health, Inc.
Any reproduction in part or whole without the written permission of Noctrix Health, Inc. is prohibited.

 NOCTRIX HEALTH	Clinical Trial Investigational Plan, Protocol CT-03 (Opioid Reduction Study)	Document #: CT-2 (Previously CT-03) Rev: 4.0 (Superseded Rev C) CC#: 720 (Previously DCO #138) Effective: 09/24/2021
---	---	---

In addition to verbatim terms, the Sponsor may categorize all AEs using MedDRA preferred terms (PT) and system organ classes (SOC). Analysis may report both verbatim and MedDRA terms.

7.1. Adverse Event Definitions

An **adverse event (AE)** is any untoward medical occurrence, independent of its association with the investigational device. AEs also include any adverse laboratory signs or physical exam findings.

A **serious adverse event (SAE¹)** is any AE that:

- led to a death,
- led to a serious deterioration in the health of the subject that:
- resulted in a life-threatening illness or injury,
- resulted in a permanent impairment of a body structure or a body function,
- required in-patient hospitalization or prolongation of existing hospitalization,
- resulted in medical or surgical intervention to prevent permanent impairment to body structure or a body function
- or led to fetal distress, fetal death or a congenital abnormality or birth defect.

A **device-related SAE** is an event meeting the SAE definition above that is also rated as probably or definitely related the investigational device. No device-related SAEs have been reported in prior studies.

Note that an elective or pre-planned hospitalization for a condition that did not worsen during the study is not an AE.

An **unanticipated serious adverse device effect (USADE)** is any SAE that is caused by, or associated with, a device, if that effect, problem, or death was not previously identified in nature, severity, or degree of incidence in the investigational plan or application (including a supplementary plan or application).

7.2. AE Severity and Relatedness

¹ Definition from ISO14155:2011

CONFIDENTIAL

 NOCTRIX HEALTH	Clinical Trial	Document #: CT-2 (Previously CT-03) Rev: 4.0 (Superseded Rev C) CC#: 720 (Previously DCO #138) Effective: 09/24/2021
	Investigational Plan, Protocol CT-03 (Opioid Reduction Study)	

Each AE occurring in the study will be characterized by the study Investigator as to severity (Table 1) and relatedness (Table 2).

Table 1. AE Severity Grading System.

Grade	Brief description
Grade 1	Mild; asymptomatic or mild symptoms; clinical or diagnostic observations only; intervention not indicated
Grade 2	Moderate; minimal, local, or non-invasive intervention indicated; limiting age-appropriate instrumental ADL ^a
Grade 3	Severe or medically significant but not immediately life-threatening; hospitalization or prolongation of hospitalization indicated; disabling; limiting self-care ADL ^b
Grade 4	Life-threatening consequences; urgent intervention indicated
Grade 5	Death related to adverse event

^a'Instrumental ADL' refers to activities of daily living such as preparing meals, shopping for groceries or clothes, using the telephone, and managing money. ^b'Self-care ADL' refers to bathing, dressing and undressing, feeding oneself, using the toilet, taking medications, and not being bedridden. From the National Cancer Institute Common Terminology Criteria for Adverse Events v4.0 NCI, NIH, DHHS. May 29, 2009 NIH publication #- 09-7473.

Table 2. AE Relatedness Grading System.*

Grade	Relationship of AE to study device	Description
5	Definite	An event that follows a reasonable temporal sequence from administration of the study device; that follows a known or expected response pattern to the study device; and that is confirmed by improvement on stopping.

CONFIDENTIAL

All information contained in this document is confidential and is the sole property of Noctrix Health, Inc.
Any reproduction in part or whole without the written permission of Noctrix Health, Inc. is prohibited.

 NOCTRIX HEALTH	Clinical Trial	Document #: CT-2 (Previously CT-03) Rev: 4.0 (Superseded Rev C) CC#: 720 (Previously DCO #138) Effective: 09/24/2021
	Investigational Plan, Protocol CT-03 (Opioid Reduction Study)	

4	Probable	An event that follows a reasonable temporal sequence from administration of the study device; that follows a known or expected response pattern to the study device; and that is unlikely to have been caused by concurrent/underlying illness or other drugs, procedures, or other causes.
3	Possible	An event that follows a reasonable temporal sequence from administration of the study device; that follows a known or expected response pattern to the study device; but may have been caused by concurrent/underlying illness, drugs, procedure, or other causes.
2	Unlikely	An event that does not follow a reasonable temporal sequence from administration of the study device; that does not follow a known or expected response pattern to the study device, or most likely was caused by concurrent/underlying illness, drugs, procedure, or other causes, because of their known effects.
1	Not related	An event almost certainly caused by concurrent/underlying illness, drugs, procedure, or other causes.

* *AEs occurring before treatment with the study device will be categorized as unrelated to the study device.*

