17.2.2. Safety Analysis

AEs occurring at any time during the study will be described and the investigator or designee will grade its severity, its relationship to device usage, and its relationship to opioid withdrawal.

The frequency of the following categories of AEs will be determined: device-related AEs, AEs related to opioid withdrawal, AEs unrelated to opioid withdrawal, SAEs. Additionally, side-effects related to baseline opioid usage, which were present at study entry, will be tracked weekly to detect potential improvement during opioid reduction and thus evaluate Endpoint 5.

Device-related will be defined as a relatedness grade of 3, 4, or 5.

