17.2.3. Criterion for Success

No Grade 3 or higher device-related adverse events and fewer than 20% of subjects with Grade 2 device-related adverse events.

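### Table 2 makes a recognised response pattern a condition of every device-related grade, so, read literally, a device effect of a new type cannot enter the safety success criterion

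*Combined protocol and SAP*

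**What the plan says.** Section 7.2 has the investigator rate every adverse event for relatedness using Table 2. The three upper grades each combine a timing condition with a pattern condition:

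- Definite (5): an event "that follows a known or expected response pattern to the study device; and that is confirmed by improvement on stopping".
- Probable (4): an event "that follows a known or expected response pattern to the study device; and that is unlikely to have been caused by concurrent/underlying illness" or another cause.
- Possible (3): an event "that follows a known or expected response pattern to the study device; but may have been caused by concurrent/underlying illness" or another cause.

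Unlikely (2) is the only row that mentions a missing pattern. After a clause on timing, it covers an event "that does not follow a known or expected response pattern to the study device, or most likely was caused by" something else. Not related (1) is kept for events almost certainly due to another cause.

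Section 17.2.2 then states: "Device-related will be defined as a relatedness grade of 3, 4, or 5". The success rule in 17.2.3 is: "No Grade 3 or higher device-related adverse events and fewer than 20% of subjects with Grade 2 device-related adverse events". Safety Endpoint 1 (17.2.1) and the definition of a device-related SAE (7.1) use a higher threshold, Probable or Definite.

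Section 7.1 also defines a USADE as a serious device effect that "was not previously identified in nature, severity, or degree of incidence in the investigational plan or application". Section 6.1 lists anticipated observations: skin irritation, discomfort or paresthesia, interference with sleep, and a temporary rise in RLS symptoms. It describes them as effects "which are typically mild to moderate, transient in nature, and resolve over time". Table 2 does not refer to 6.1, and the plan does not define what makes a pattern known or expected.

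**The concern.** A relatedness scale for an investigational device has to be able to attribute to the device something nobody has seen before. This one makes prior recognition of the pattern a requirement for every grade that counts. The plan itself accepts, through the USADE definition, that an effect not previously identified can be caused by the device, but Table 2 offers no device-related grade for an effect that is new in nature.

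At stake is the meaning of a safety pass. The criterion in 17.2.3 could be met while device-caused events of a new type occur, because the rating rule keeps them out of the count. With up to four sites and an undefined term, two investigators could also grade the same new event differently.

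**Working it through.** The plan gives no figure on this point to reproduce. The check is mainly of definitions, followed by an illustration.

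**Step 1: the pattern condition.** It appears in Definite, Probable and Possible, so 3 of the 3 grades that 17.2.2 counts carry it, in each case in addition to the timing condition.

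**Step 2: a test event.** Take an event that begins after stimulation, has no clear other cause and is of a type not previously identified.

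- Definite: timing met, pattern not met. It fails, even if the event stops when the device is removed.
- Probable: timing met, pattern not met. It fails, even though another cause is unlikely.
- Possible: timing met, pattern not met. It fails.
- Unlikely: if the clauses are alternatives, the missing pattern is enough and the event is grade 2. If the timing and pattern clauses must both apply, the event does not fit, because its timing is reasonable.
- Not related: it fails, because no other cause is almost certain.

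The event is therefore grade 2 or has no row. On neither reading is it grade 3, 4 or 5.

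**Step 3: where the grade is used.** The event is outside the device-related count in 17.2.2 and outside both parts of the criterion in 17.2.3. It is outside Safety Endpoint 1 and the device-related SAE definition, which need grade 4 or 5. It is outside Safety Endpoint 2, which states no threshold of its own, on either threshold used in the plan.

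**Step 4: other routes.** Section 10.7 has the sponsor assess each SAE for USADE status. The outcome leads to reporting and possible termination; nothing returns it to the Table 2 grade or to 17.2.3. It also covers SAEs only. A Grade 2 event, or a Grade 3 event that does not meet the SAE definition, has no such assessment. The sponsor's confirmation of relatedness in 10.7 names no other scale.

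**Step 5: illustration.** N = 20 to 40 (Synopsis, primary study). Let p be the per-subject probability of a new-type, device-caused event of Grade 3 or higher. The values of p are assumptions; the documents give none. Assume that subjects are independent and that no other device-related events occur.

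P(at least one such event) = 1 − (1 − p)^N; P(zero-event rule met if these events were counted) = (1 − p)^N.

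| p (assumed) | N | P(at least one) | P(rule met if counted) | P(rule met as written) |
|---|---|---|---|---|
| 2% | 20 | 0.332 | 0.668 | 1 |
| 5% | 20 | 0.642 | 0.358 | 1 |
| 10% | 20 | 0.878 | 0.122 | 1 |
| 2% | 40 | 0.554 | 0.446 | 1 |
| 5% | 40 | 0.871 | 0.129 | 1 |
| 10% | 40 | 0.985 | 0.015 | 1 |

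For the Grade 2 part, fewer than 20% means at most 3 of 20 (15%) or 7 of 40 (17.5%). If new-type Grade 2 effects had assumed per-subject rates of 10%, 20% or 30% and were counted, binomial probabilities of staying within the limit would be 0.867, 0.411 and 0.107 for N = 20, and 0.958, 0.437 and 0.055 for N = 40. As written, such effects leave the probability at 1.

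**The case against.** The strongest reply is that the term is undefined and need not be read narrowly. Table 2 does not point to 6.1, and 6.1 speaks of anticipated observations, a different term. Section 1.5 likens the device's output to TENS and functional stimulators, so an investigator could reasonably treat an effect typical of that class as expected and grade it Possible or higher. This stands in part: the gap is confined to events that are neither known nor reasonably expectable. It does not close the gap, because nothing in the plan tells raters to read the term broadly.

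A second reply is that an event fitting no row is ungraded rather than graded as unrelated, and is left to the investigator and to the review in 10.7. That is fair as a description. But an ungraded event is still not grade 3, 4 or 5, and the plan gives no default.

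A third is that such events are not lost. This is correct. Section 7 records and summarises all adverse events, the sponsor reviews all of them, 17.2.2 describes each one and tabulates those unrelated to opioid withdrawal, withdrawal because NPNS is not tolerated is counted without Table 2 (17.3), and 16.13 lets the sponsor stop for an unexpectedly high rate of unexpected events. None of this feeds 17.2.3.

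Two stronger readings are tempting and should not be drawn. A reader might infer from the words typically mild to moderate in 6.1 that a severe device effect also cannot be attributed. The documents do not support that: severity is graded separately in Table 1, so severe skin irritation, for example, can be Grade 3 and Definite and would fail the criterion. For the same reason, the conflict with the USADE definition is limited to effects new in nature, not those unanticipated only in severity or incidence. A reader might also infer that unexpected harm would go unreported; the recording and SAE provisions show otherwise.

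**Conclusion.** The point holds as a defect in the relatedness scale and in what depends on it. On a literal reading of Table 2, an event of a new type with plausible timing and no clear other cause cannot reach grade 3, 4 or 5, so it is left out of the device-related count, the NPNS-related safety endpoints and the 17.2.3 criterion.

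Its contribution to the criterion is zero at any true rate. How often that would matter cannot be judged from the documents: the probabilities above rest on assumed rates and apply to the zero-event rule only when they refer to events of Grade 3 or higher. Section 7.1 reports no device-related SAEs in prior studies, but that says nothing about non-serious events.

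The conclusion assumes literal use of the table and no correction on sponsor review. Given those conditions, and an exploratory study in which all events are still recorded and reviewed, this is something that should be fixed, not a critical flaw.

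**What to change.** In Table 2:

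- Possible: remove the pattern condition as a requirement, so that reasonable timing is enough even if another cause may explain the event.
- Probable and Definite: change the condition to *a known, expected or plausible response pattern*.
- Unlikely: delete the pattern clause, leaving timing and a more likely other cause.

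In 17.2.2, add one sentence: any event that the sponsor determines to be a USADE counts as device-related in the safety endpoints and in 17.2.3.

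For Possible, it is better to remove the condition than to add an alternative based on having no more likely other cause, because that would clash with the row's own allowance for another cause.

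The cost is wording in one table and one sentence, with no new data collection. The downside is that a few more events may be rated Possible, so the device-related figure may look slightly less favourable. The change does not settle the separate difference between the threshold in 17.2.2 (grades 3 to 5) and the one in Safety Endpoint 1 (Probable or Definite), which could be aligned in the same amendment.

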7.3. Adverse Event Reporting

Investigators must report all SAEs to the study Sponsor and governing IRB within 3 business days or according to local IRB guidelines. Investigators should call the study sponsor immediately upon becoming aware of the occurrence of an SAE. The sponsor will contact the independent medical reviewer, to assist in assessing any safety concerns, if needed. The Investigator should be able and willing to provide further information on the specific event when requested by the study Sponsor. If the Investigator learns of an SAE that occurs within 1 month after the subject completes the study, he/she should notify the Sponsor. Investigators must also report all AEs to the governing IRB as determined by that IRB.

Prompt AE evaluation:

- protects the safety of study subjects;
- aids in understanding the overall safety profile of the device;

CONFIDENTIAL

All information contained in this document is confidential and is the sole property of Noctrix Health, Inc.
Any reproduction in part or whole without the written permission of Noctrix Health, Inc. is prohibited.

 NOCTRIX HEALTH	Clinical Trial Investigational Plan, Protocol CT-03 (Opioid Reduction Study)	Document #: CT-2 (Previously CT-03) Rev: 4.0 (Superseded Rev C) CC#: 720 (Previously DCO #138) Effective: 09/24/2021
---	---	---

- prompts, if necessary, modification to the study protocol
- allows improvements in study design or procedures; and
- adheres with standard good clinical practices.

8. Device Tracking

The Sponsor will send the Investigator investigational devices. The Investigator must house study devices in a secure location.

The Investigator must carefully and completely track receipt, use and disposition of all investigational devices. The Sponsor will track sending and receiving of devices. The Sponsor will monitor site device accountability periodically.

If a Sponsor representative or designee is present at the time of use, he/she may directly take possession of used device(s). All devices will be returned to the Sponsor after the study is complete.

9. Device Deficiencies and Malfunctions

Throughout the study, the Investigator and study staff will report and document all device deficiencies and malfunctions related to the identity, quality, durability, reliability, safety or performance of the device. This includes reporting of device deficiencies/malfunctions that did not lead to an AE but could have if: 1) suitable action had not been taken, 2) intervention had not been made, or 3) circumstances had been less fortunate. If possible, the Investigator should return devices suspected of deficiency or malfunction to the Sponsor for analysis.

10. Ethical and Regulatory Considerations

